| | | Section 11. Updated Reimbursement |
| | | to include Travel Expenses |
| Version 4.0 | 17Jan2024 | Update Title Page with new CTCC PI |
| | | Information |
| | | Removed Investigator Agreement |
| | | Page |
| | | Synopsis: Updated number of |
| | | participant enrolled from 5000 to |
| | | 2000 |
| | | SOA: Added UPSIT |
| | | Section 5: Changed "will" to "may" |
| | | with regard to Recruitment activities |
| | | log collection |
| | | Section 7.1: Added information |
| | | about the UPSIT Test and procedures |
| | | Section 13. Removed Participant |
| | | Withdrawals as Reportable Events |

RSRB Study Number: 00006240

Page 3 of 24 Version 5.0

| | | Section 15. Added Specimens may be shared with Psomagen, Inc., Section 20. Added information about |
|-------------|-----------|--|
| Version 5.0 | 07Feb2024 | _ |
| | | UPSIT/replaced with SIT Section 7.2: addition of Tasso+ as blood collection option, increase in remuneration, companion travel reimbursement language |

BLAAC PD PROTOCOL SYNOPSIS

| Protocol Title Black and African Americans Connections to Parkinson's Disease | |
|---|----------|
| Acronym/Working Title | BLAAC PD |

RSRB Study Number: 00006240

Page 4 of 24 Version 5.0

| Spansor | Aligning Science Across Parkinson's | |
|-----------------------------------|---|--|
| Sponsor | Aligning Science Across Parkinson's; The Michael J. Fox Foundation for Parkinson's Research | |
| Clinical Phase | Observational | |
| Investigators | Multi-Center Trial | |
| Study Centers | Up to approximately 12 clinical research sites located in the Continental United | |
| | States. | |
| Study Period | Five (5) Years - Ten (10) Years with a 1-year trial enrollment period to assess sample | |
| | size feasibility. | |
| Study Objective and Specific Aims | The general aim of this project is to dissect the genetics of Parkinson's disease (PD) among the Black and African American population. Analyses seek to identify similarities and/or differences related to genetic data collected from other populations that may provide evidence for application of therapies in development and may illuminate novel targets for additional investigation. | |
| | , | |
| | 1.1 Primary Objectives: To dissect the genetics of Parkinson's disease (PD) among the Black and African American population | |
| | The Specific Aims of this study are: Screening of pathogenic variants present in the NeuroBooster (previously NeuroPlus) Array Genotyping Platform and analysis of their frequencies in the African or African admixed population. Genome-wide assessment involving cumulative risk score calculation versus disease status and age at onset and comparison with European populations and heritability calculation. Pilot analysis of trans-ethnic fine-mapping and admixture mapping to establish analysis pipelines for future larger studies. Conduct genetic-phenotypic correlations to understand the relationship between genetic variation and observable clinical traits (like dementia) in these populations Develop and systematically test strategies that enable recruitment of Black Americans and African Americans to participate in PD genetics research | |
| Study Population | Black Americans and African Americans with Parkinson's Disease or without a history of parkinsonism (control participants). | |
| Study Design | This is a multi-center observational study. | |
| Number of Participants | Up to 2,000 participants with Parkinson's Disease (PD) and up to 2,000 healthy | |
| | controls self-identifying as Black and/or African American. | |
| Inclusion Criteria | Inclusion Criteria for Participants with Parkinson's disease: | |
| | Willing and able to provide informed consent or have a legally authorized representative to provide consent | |
| | Willing and able to complete all study activities | |
| | Age 18 years or older | |
| | Self-identify as Black or African American | |
| | Meet the Movement Disorder Society's diagnostic criteria for Parkinson's disease | |
| | English speaking | |

RSRB Study Number: 00006240

Page 5 of 24 Version 5.0

| | Inclusion Criteria for Control Participants: Willing and able to provide informed consent or have a legally authorized representative to provide consent Willing and able to complete all study activities Age 18 years or older Self-identify as Black or African American English speaking | |
|-------------------------------|---|--|
| Exclusion Criteria | Exclusion Criteria for Participants with Parkinson's disease: | |
| | Exclusion Criteria for Control Participants: Diagnosis of the following disorders: Parkinson's disease, Alzheimer's disease, Frontotemporal dementia, Corticobasal syndrome, Dementia with Lewy bodies, Motor neuron disease, Multiple system atrophy, Progressive supranuclear palsy, Spinocerebellar Ataxia (SCA), REM sleep behavior disorder, Any other parkinsonian disorder or dementia NOS Familial history of any of the following disorders in a 1st degree relative (participant's parent, sibling or child): Parkinson's disease, Alzheimer's disease, Frontotemporal dementia, Corticobasal syndrome, Dementia with Lewy bodies, Motor neuron disease, Multiple system atrophy, Progressive supranuclear palsy, Spinocerebellar Ataxia (SCA), REM sleep behavior disorder, Any other parkinsonian disorder or dementia NOS Any condition that, in the investigator's opinion, precludes the individual's ability to carry out study activities | |
| Primary Outcome Measures | Novel risk factors and characterization of known genetic risk factors contributing to PD risk in the Black or African American population. | |
| Sample Size Considerations | The study aims to recruit up to 2000 participants with PD and up to 2,000 controls. Power calculations were performed using the GAS power calculation tool by Abecasis et al. Our power to detect an association between common genetic variation (minor allele frequency < 5%) and PD risk was estimated to be 99.8% considering a general disease prevalence = 0.1% (Tysnes et al 2017) and a genotype relative risk effect = 1.5 when including 2,000 cases and 2,000 controls at a significance p-value < 5×10-8 assuming the limitation that the genetic architecture in the Black and/or African American ancestry is unknown. | |

BLAAC PD SCHEDULE OF ACTIVITIES

| Activity | Cases | Controls |
|-----------------------|-------|----------|
| Informed Consent | х | Х |
| Participant ID Number | х | Х |
| Demographics | Х | х |
| Inclusion/Exclusion | х | Х |

RSRB Study Number: 00006240

Page 6 of 24 Version 5.0

| Activity | Cases | Controls |
|--------------------------------------|-------|----------|
| Recruitment source questionnaire | X | Х |
| Family history questionnaire | х | Х |
| PD Features | х | |
| CISI-PD | х | |
| REM sleep behavior disorder question | х | Х |
| MDS UPDRS item 1.12 | х | Х |
| Environmental exposure questionnaire | х | Х |
| Montreal Cognitive Assessment | х | Х |
| Reportable Events | х | Х |
| Biosample Collection | х | Х |

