3. STUDY DESIGN

The Global Parkinson's study is a project of the Genetics Program (GP2, https://parkinsonsroadmap.org/gp2/), which is part of the Aligning Science Across Parkinson's initiative (ASAP, https://parkinsonsroadmap.org/), and is Implemented by the Michael J. Fox Foundation for Parkinson's Research. GP2 is an international effort aimed at generating significant insight into the genetic basis of PD and democratizing access to results and data. GP2 is funded by ASAP and is part of the core ASAP strategic objectives which include: support collaboration, generation of resources and democratize data. The GP2 initiative is funded through 2030.

The Michael J. Fox Foundation for Parkinson's Research (MJFF) is the ASAP implementation partner and is supporting its various efforts including GP2 and BLAAC PD.

BLAAC PD aims to generate phenotypic and genetic data on a cohort of at least 1000 and up to 2,000 PD (including familial/sporadic PD cases) and at least 1000 and up to 2,000 control Black and African American participants. While this sample size is modest compared to similar studies of PD risk in White populations, it will constitute the largest sample ever aggregated of Black and African American Parkinson's participants and will therefore be a foundation for future collection efforts to generate even greater sample sizes.

Recruitment, engagement and retention materials will be provided by MJFF. A biorepository and/or gene sequencing center contracted with MJFF, on behalf of GP2, will be providing biosample storage and management along with performing testing and analyses. Database creation and management will take place through a management center contracted with MJFF, on behalf of GP2. The Clinical Trials Coordination Center (CTCC) department in Center for Health and Technology (CHeT) at the University of Rochester Medical Center (URMC) will be providing site management and data monitoring.

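### The stated 99.8% power does not follow from its own inputs: at a minor allele frequency of 5% they give about 13% at best, and less below that.

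*Protocol*

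**What the plan says.** The Synopsis (Sample Size Considerations) gives one power figure: "Our power to detect an association between common genetic variation (minor allele frequency < 5%) and PD risk was estimated to be 99.8" per cent. The inputs printed with it are:

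- prevalence: "considering a general disease prevalence = 0.1" per cent
- effect: "a genotype relative risk effect = 1.5"
- sample: "when including 2,000 cases and 2,000 controls"
- threshold: "at a significance p-value < 5×10-8"
- tool: "Power calculations were performed using the GAS power calculation tool"

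The genetic model entered in the tool is not stated. The one caveat is that the genetic architecture in this ancestry is unknown. No other section gives a power figure.

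Section 3 (Study Design) sets the cohort at "at least 1000 and up to 2,000 PD (including familial/sporadic PD cases) and at least 1000 and up to 2,000 control" participants, so 1,000 per group is also an accepted size.

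**The concern.** The phrase "common genetic variation (minor allele frequency < 5" per cent contradicts itself, since variants below 5% are not usually called common; the sign may be a slip. The larger problem is the number. A GRR of 1.5 at a genome-wide threshold with 2,000 per group is demanding at low allele frequency, and near-certain detection there is implausible.

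The figure matters because the primary outcome is the identification and characterisation of genetic risk factors, and Section 20 tests each imputed variant for association. Someone relying on 99.8% could read the absence of a genome-wide hit at a low-frequency variant as near-exclusion of a GRR 1.5 effect there.

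**Working it through.** **Inputs.** From the Synopsis: GRR g = 1.5, prevalence K = 0.001, 2,000 cases and 2,000 controls (4,000 alleles per group), α = 5×10⁻⁸, MAF p = 0.05 as the most favourable limit of the stated range. Assumptions, because the protocol is silent: Hardy-Weinberg proportions, a two-sided allelic test with a normal approximation, and each of four genetic models in turn.

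**Formulas (multiplicative model).**

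- Case allele frequency: p₁ = g·p / (1 + (g − 1)·p)
- Control allele frequency: p₀ = (p − K·p₁) / (1 − K)
- z = (p₁ − p₀) / √[p₁(1 − p₁)/4000 + p₀(1 − p₀)/4000]
- Power = Φ(z − 5.451), where 5.451 is the two-sided critical value at 5×10⁻⁸

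**Attempt to reproduce 99.8% at MAF 5%.**

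- p₁ = 0.075 / 1.025 = 0.0732
- p₀ = (0.05 − 0.001 × 0.0732) / 0.999 = 0.0500
- Standard error = √[(0.0678 + 0.0475) / 4000] = 0.00537
- z = 0.0232 / 0.00537 = 4.32
- Power = Φ(4.32 − 5.45) = Φ(−1.13) = **12.9%**

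The figure is not reproduced. A pooled variance gives 12.8% and a one-sided test 15.7%. Other models give less: additive 11.0%, dominant 7.9%, recessive about 0%.

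**Power across MAF at 2,000 per group (GRR 1.5, two-sided).**

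| MAF | Multiplicative | Additive | Dominant |
|---|---|---|---|
| 0.01 | 0.03% | 0.03% | 0.02% |
| 0.03 | 2.0% | 1.8% | 1.4% |
| 0.05 | 12.9% | 11.0% | 7.9% |
| 0.10 | 67% | 57% | 37% |
| 0.15 | 93% | 86% | 57% |
| 0.20 | 99% | 95% | 64% |
| 0.26 | 99.8% | 98% | 62% |

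Under the multiplicative model power passes 50% at MAF of about 0.084, 80% at about 0.12 and 99.8% at about 0.26, and stays above 99.8% from there to 0.50. The additive model passes 50% at about 0.092 and 80% at about 0.14, and peaks near 99.0%. The dominant model peaks near 64%, and the recessive model reaches about 32% at MAF 0.50.

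**Could a changed input explain 99.8% at MAF 5%?** Multiplicative model, one change at a time:

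- Prevalence 0.05% to 2%: 12.8% to 14.9%. Prevalence 10%: 27%.
- 5,000 per group (5,000 is the number enrolled before the Version 4.0 change): 91.6%.
- α = 0.05 in place of 5×10⁻⁸: 99.1%.
- Sample needed for 99.8%: 2,000 × [(5.451 + 2.878) / 4.320]² ≈ 7,430 per group.
- GRR needed for 99.8% at 2,000 per group: about 2.08. For 80%: about 1.77.

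**Minimum cohort, 1,000 per group (multiplicative).** Power is 0.8% at MAF 0.05 and 50% at 0.20, and is at most about 84% at any MAF. Reaching 80% needs MAF of about 0.35, or GRR of about 2.17 at MAF 0.05.

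**The case against.** - **The sign is a slip for "greater than".** This is plausible, and it removes the contradiction with the word common. It does not rescue the figure: just above 5% power is still about 13%, and at MAF 0.10 it is 67%.
- **The calculation may have been run correctly at some other MAF.** This stands as a possibility. A multiplicative model at MAF of about 0.26 returns 99.8%. The defect would then lie in how the result is described. The documents do not show what was entered, so neither a faulty run nor a particular intended MAF can be inferred.
- **The study is well powered for most common variants.** This is right at 2,000 per group under the multiplicative and additive models. A reader might infer from the 13% that the study would usually miss GRR 1.5 effects over most of the frequency range. The table contradicts that: under the multiplicative model, detection is more likely than not from MAF of about 0.08, and power is 93% at 0.15.
- **Controls may be supplemented.** Section 20 allows public control data. With an assumed 10,000 controls and 2,000 cases, power at MAF 5% rises to about 43%, still far from 99.8%.
- **The caveat and the wider aims.** The unknown genetic architecture qualifies the inputs, but it does not make those inputs yield 99.8%. The risk score, heritability, gene-based and recruitment aims do not rest on single-variant power, so the error does not undermine them.
- **The minimum cohort is a separate matter.** The figure is openly conditioned on 2,000 per group, and Section 3 calls the sample modest and a foundation for later collections. Giving no figure for 1,000 per group is not an arithmetic error; asking for one is secondary.

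**Conclusion.** The stated power is wrong as written. At MAF 5% the protocol's inputs give about 13%, 11%, 8% or about 0% depending on the genetic model, against a stated 99.8%, and power falls towards zero below 5%. The result rests on Hardy-Weinberg proportions and an allelic test with a normal approximation. It does not depend on the unstated genetic model, on sidedness (15.7% at most) or on the choice of variance.

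Reversing the inequality leaves a claim that is true only from MAF of about 0.26 upward, and only under the multiplicative model.

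The practical reach is limited. Under the multiplicative model, GRR 1.5 variants are more likely missed than detected below MAF of about 0.08. A reader might go further and treat any null result below the 80% limits as uninformative. That is too strong: at MAF 0.10, below the limit of about 0.12, power is still 67%. Nor does the finding show that the sample is too small for the study's stated purpose. Because this is the protocol's only sample-size justification, it should be corrected.

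**What to change.** In the Synopsis, Sample Size Considerations:

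1. Delete the 5% limit on allele frequency.
2. Have the sponsor state the MAF and genetic model entered in the calculator, and rerun it.
3. Replace the single figure with power by MAF. If the model is multiplicative, at 2,000 per group and GRR 1.5 this is about 13% at MAF 0.05, 67% at 0.10, 93% at 0.15, 99% at 0.20 and 99.8% from about 0.26. Add that 80% power needs MAF of about 0.12 or more, or GRR of about 1.77 at MAF 0.05.
4. As a secondary addition, give the same figures for the 1,000 per group minimum in Section 3: 0.8% at MAF 0.05, 50% at 0.20, at most about 84%.
5. Say that a null single-variant result at a MAF where power is low is not evidence against a GRR 1.5 effect.

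The cost is wording and a less favourable stated power. No participants, procedures or analyses change.

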1. BACKGROUND AND RATIONALE

A major limitation in Parkinson's disease (PD) genomics research is lack of diversity, specifically lack of inclusion of data from the Black and African American population. Enhanced genetics research with this population may enable the identification of a broad range of genetic variation that could elucidate disease mechanisms and inform genetic tests and drug development, specifically for members of this community. Additionally, fine-mapping across Black and African Americans could be extremely useful given the allelic diversity and linkage disequilibrium patterns to identify putative functional variants that can provide insights applicable to a broader disease landscape.

The general aim of this project is to dissect the genetics of PD in the Black and African American population. Deciphering causal and genetic risk factors will help researchers understand if the potential targets for a disease-modifying treatment or prevention strategies that are under investigation in populations of European ancestry are relevant to Black and African Americans, filling a gap of knowledge existing in PD genetics in a valuable and underserved population. This pioneering initiative will give rise to the generation of valuable data for future projects within the Global Parkinson's Genetics Program (GP2) and beyond.

2. PURPOSE OF STUDY

The general aim of this project is to dissect the genetics of Parkinson's disease (PD) among the Black and African American population. Analysis seeks to identify similarities and/or differences related to genetic data collected from other populations that may provide evidence for application of therapies in development and may illuminate novel targets for additional investigation.

Specific aims:

- 1. Screening of pathogenic variants present in the NeuroBooster (previously NeuroPlus) Array Genotyping Platform and analysis of their frequencies in African or African admixed populations
- Genome-wide assessment involving cumulative risk score calculation versus disease status, age at onset and SIT scores, and comparison with other populations and heritability calculation.
- 3. Pilot analysis of trans-ethnic fine-mapping and admixture mapping to establish analysis pipelines for future larger studies. By using ~5K ancestry informative markers on the NeuroBooster array that tag regions that are highly variable between European and African populations, local ancestry methods can be utilized to increase our statistical power exponentially with regard to association signals possibly harbored within these regions based on differential linkage disequilibrium signatures. We and others have successfully employed admixture methods for localization of association signals and fine mapping of loci including in sample sizes similar to that proposed here. If summary data are available for other continental ancestries, these data can also be leveraged in terms of trans-ethnic fine mapping to possibly identify novel loci as well as refine credible intervals around known loci.
- 4. Conduct genetic-phenotypic correlations to understand the relationship between genetic variation and observable clinical traits (like dementia) in these populations.
- 5. Develop and systematically test strategies that enable recruitment of Black Americans and African Americans to participate in PD genetics research

RSRB Study Number: 00006240

Page 9 of 24 Version 5.0

3. STUDY DESIGN

The Global Parkinson's study is a project of the Genetics Program (GP2, https://parkinsonsroadmap.org/gp2/), which is part of the Aligning Science Across Parkinson's initiative (ASAP, https://parkinsonsroadmap.org/), and is Implemented by the Michael J. Fox Foundation for Parkinson's Research. GP2 is an international effort aimed at generating significant insight into the genetic basis of PD and democratizing access to results and data. GP2 is funded by ASAP and is part of the core ASAP strategic objectives which include: support collaboration, generation of resources and democratize data. The GP2 initiative is funded through 2030.

The Michael J. Fox Foundation for Parkinson's Research (MJFF) is the ASAP implementation partner and is supporting its various efforts including GP2 and BLAAC PD.

BLAAC PD aims to generate phenotypic and genetic data on a cohort of at least 1000 and up to 2,000 PD (including familial/sporadic PD cases) and at least 1000 and up to 2,000 control Black and African American participants. While this sample size is modest compared to similar studies of PD risk in White populations, it will constitute the largest sample ever aggregated of Black and African American Parkinson's participants and will therefore be a foundation for future collection efforts to generate even greater sample sizes.

Recruitment, engagement and retention materials will be provided by MJFF. A biorepository and/or gene sequencing center contracted with MJFF, on behalf of GP2, will be providing biosample storage and management along with performing testing and analyses. Database creation and management will take place through a management center contracted with MJFF, on behalf of GP2. The Clinical Trials Coordination Center (CTCC) department in Center for Health and Technology (CHeT) at the University of Rochester Medical Center (URMC) will be providing site management and data monitoring.

4. INCLUSION AND EXCLUSION CRITERIA

Inclusion Criteria for Participants with Parkinson's disease:

- Able and willing to provide informed consent or have a legally authorized representative to provide consent
- Age 18 or older
- English speaking
- Self-identify as Black or African American
- Meet the Movement Disorder Society's diagnostic criteria for Parkinson's disease

Exclusion Criteria for Participants with Parkinson's disease:

 Any condition that, in the investigator's opinion, precludes the individual's ability to carry out study activities

Inclusion Criteria for Control Participants:

 Able and willing to provide informed consent or have a legally authorized representative to provide consent

RSRB Study Number: 00006240

Page 10 of 24 Version 5.0

- Willing and able to complete all study activities
- Age 18 years or older
- English speaking
- Self-identify as Black or African American

Exclusion Criteria for Control Participants:

- Diagnosis of Parkinson's disease and/or any of the following disorders: Alzheimer's disease, Frontotemporal dementia, Corticobasal syndrome, Dementia with Lewy bodies, Motor neuron disease, Multiple system atrophy, Progressive supranuclear palsy, Spinocerebellar Ataxia, REM sleep behavior disorder, or any other parkinsonian disorder or dementia NOS
- Familial history of PD and/or any of the following disorders: Alzheimer's disease,
 Frontotemporal dementia, Corticobasal syndrome, Dementia with Lewy bodies, Motor neuron disease, Multiple system atrophy, Progressive supranuclear palsy, Spinocerebellar Ataxia, REM sleep behavior disorder, or any other parkinsonian disorder or dementia NOS
- Any other condition that, in the investigator's opinion, precludes the individual's ability to carry out study activities

